- Does participation in the TRAC intervention lead to improvements in medication adherence?

- Does participation in the TRAC intervention impact other clinical HIV outcomes, including CD4 count and viral load?

3. Study Objectives

The aim of the study is to conduct a pilot randomized controlled trial of the TRAC intervention among PLWHA:

- Two-month, randomized-controlled waitlist trial with 2-month follow-up ($N=50$)
- Feasibility evaluation, focusing on recruitment, engagement, and adherence
- Evaluation of effects on overall alcohol consumption, HAART adherence, and clinical outcomes

4. Study Design

Description of relevance to the VA

HIV occurs among veterans at a higher rate than among those in the general population. Moreover, many veterans struggle with alcohol use disorders, which can impact their health and overall quality of life. The TRAC intervention, which aims to reduce alcohol use among people living with HIV/AIDS, thus meets two important needs among the VA patient population.

Study Population and patient selection

Subject Inclusion Criteria: To be eligible to participate in the intervention, patients must be 1) HIV-positive, 2) 18 years and older, 3) an at-risk drinker as identified through a screening procedure, 4) currently taking HIV medication and 5) a patient receiving care at one of the study recruitment sites. Based on NIAAA's screening recommendations, every person living with HIV who reports to participating clinics will complete a short screening procedure. Clinical data of interest including alcohol dependency diagnoses and prescription use will be pulled from CDW via VINCI, CCR and HAVACS. These clinical indicators will be used to create a list of eligible patients with appointments in the coming month for screening. The list of eligible patients will be stored in the secure VINCI project folder and then downloaded to the secure local VA drive for use by study coordinators. The only two locations in which the list will be stored are within VINCI and on the secure local drive. After a list of patients has been created, the study coordinator will screen the patient EMR (CPRS/VISTA) for inclusion criteria.

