7. The research coordinator will check to see if the following inclusion criteria are met:
 - a. HIV-positive
 - b. 18 years or older
 - c. An at-risk drinker as identified by the alcohol screener
 - d. Currently taking HIV medication
 - e. A score less than 20 on the AUDIT questionnaire
 - i. Score is displayed on the final page of the questionnaire. If above 20, see step 9 below for further direction.
8. If patients are eligible, the research coordinator will provide them with a TRAC flyer and consent form
 - a. If the patient wants to enroll in the study, the coordinator will proceed with enrollment (see next section)
 - b. If the patient does not want to enroll today, they can take the TRAC flyer and consent form with them. If they want to enroll at a later date, they can call the VA coordinator.
 - c. They are eligible to begin the study if they enroll within 30 days. If they would like to join the study after that date, they will need to be re-screened.
9. If patients are ineligible because of a score of 20 or higher on the AUDIT questionnaire, a note will be made in their chart and a referral made to their clinical team for follow-up regarding concerning levels of alcohol use.
10. Screening activities will not collect any data to be used in the study.

Step 2: Patient Enrollment

1. The coordinator will go through the consent form and HIPAA form with the participant, discussing:
 - a. The overall purpose of the study
 - b. The time commitment of the study
 - c. Their expectations as a participant
 - d. The incentives they will receive
 - e. Any questions the participant has
2. Once the participant has demonstrated sufficient understanding of the consent and HIPAA forms, the research coordinator will obtain consent and a signature on the HIPAA form.
3. The research coordinator will assign the participant a numeric identifier and record it in the secure code key
 - a. The research coordinator will inform the participant that if they forget their study ID at any time, they can contact the researchers to learn what it is.
4. Only researchers will have access to this key, which will be kept in a password-protected file

5. The research coordinator will then check the randomization spreadsheet (pre-generated set of random numbers for each participant ID assigning them to the intervention or waitlist-control group)
 - a. If they are in the intervention group (Group 1):

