In the event that identifying information is released to an unauthorized party, the serostatus of participants could be revealed to unwanted individuals. This could potentially cause harm, but is unlikely considering the careful plans in place regarding data management and protection. All possible measures will be taken to protect information provided through surveys, interviews, and intervention participation, and confidentiality will be respected. Following completion of data collection, responses will become anonymous as identifying information is permanently deleted. For these reasons, we estimate that this minimally-invasive project poses minimal risk.

STATISTICAL ANALYSIS PLAN

For the randomized controlled trial, data analytic methods will be focused on examining acceptability and feasibility, as well as effects on alcohol intake, HAART adherence, and HIV-related medical outcomes (CD4 count and viral load). Intervention adherence, daily monitoring adherence, and session acceptability will be described using descriptive statistics. Session attitudes will be assessed using several 5-point semantic differential attitudinal measures rating the session, including Boring/Interesting, Unpleasant/Pleasant, Bad/Good, Useless/Useful, and Negative/Positive. Scores on the session attitude semantic differential measures will be reverse-coded where required and averaged to form an overall attitude score, with “0” being “neutral.”

We will provide descriptive summaries for the outcome variables, including mean, median, and standard deviation for continuous variables and counts and percentages for categorical variables. We will summarize the outcome variables overall and across the intervention groups. In assessing the differences in alcohol use and medication adherence between the two groups during the 8-week intervention period, we will utilize the Kruskal–Walli’s test, a non-parametric statistical approach, to compare the distribution of outcome variables. The general linear model (ANOVA) will be used to estimate the difference between alcohol use and medication adherence among the groups, and the estimation of the effect size (Cohen’s D) at the end of the 8-week intervention period. While this study was not powered to detect significant differences, the goal of these analyses is to observe changes and effect sizes that may provide preliminary evidence of efficacy.

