To examine intervention effects as assessed through daily surveys, we will examine responses to the morning survey question asking if participants had consumed alcohol on the previous day (yes/no), whether or not they reported a positive breathalyzer reading (> 0.0), and if they had taken all of their HAART on the previous day (yes/no). Within the 8-week intervention period and using the daily data, we will assess the change in the proportion of participant's alcohol use, the proportion of positive breathalyzer readings, and the proportion of their medication use from the beginning of week 1 to the end of week 8 using McNemar's matched pair test. This test will allow us to address the interdependency in the repeated measurements. We will account for missing survey responses by considering two scenarios: First, assuming they were missing completely at random and remained missing, and second, that missing values were indicative of alcohol use/medication nonadherence and were thus filled in as drinking days/positive breathalyzers/nonadherent days (a conservative approach).

All participants will have received the intervention by the end of the 8 week (2-month) post-intervention period. To examine long-term intervention effects, participants from both the waitlist-control and intervention group will be combined into a single dataset. A generalized linear model (via SAS GENMOD PROCEDURE) and a multiple linear regression model will be fit to the change from baseline for each outcome measure. Change from baseline is the difference between the baseline value and values obtained at subsequent time points: 8 weeks (immediate post-intervention; T2 for intervention group and T3 for waitlist-control), and 16 weeks (2 months post-intervention; T3 for intervention group and T4 for waitlist-control) for each outcome measure. The rationale for fitting the change from baseline is that this model removes the effect of baseline differences that may exist from the model. All statistical hypothesis tests will be conducted using the standard 5% significance level. SAS Version 9.4 (TS1M1, SAS Institute, Cary, NC), will be used for all analyses.

References

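### Viral load is analysed as a raw linear change from baseline in treated patients, so one or two viremic participants could dominate an unstable, uninformative estimate

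*Combined protocol and SAP*

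**What the plan says.** The opening of the Statistical Analysis Plan lists "HIV-related medical outcomes (CD4 count and viral load" among the effects to be examined. The paragraph on long-term effects pools both groups and specifies two models for the same response: "A generalized linear model (via SAS GENMOD PROCEDURE", with no distribution or link stated, and a multiple linear regression. The regression statement is general: "a multiple linear regression model will be fit to the change from baseline for each outcome measure". The response is defined as follows: "Change from baseline is the difference between the baseline value and values obtained at subsequent time points". No log scale, rule for values below an assay's reporting limit, or suppressed/not-suppressed endpoint is given.

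The Kruskal-Wallis test and the ANOVA are specified only for alcohol use and medication adherence. The McNemar tests use only the daily survey and breathalyzer data. The long-term model is therefore the only inferential analysis that reaches viral load.

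On who enters, Step 1, item 7 requires "Currently taking HIV medication". The viral load rules in Subject Exclusion Criteria and Step 2, item 5 ask for a recent or planned test and set no level. Viral load comes from retrospective chart review of routine draws, with at least two values per person. The window runs from 3 months before to 6 months after entry in the intervention group (Step 3a, item 13) and from 1 month before to 8 months after entry in the waitlist group (Step 3b, item 16).

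**The concern.** In people on HIV treatment, many viral loads can be expected at or below the reporting limit. A participant who is suppressed before the intervention cannot improve on this scale. If the person stays suppressed, the change is zero; if the person rebounds, it may be thousands of copies/mL. A mean of such differences mostly describes the few people with the largest values. It does not answer the question a reader would ask of a pilot, namely how many people were suppressed before and how many after.

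At stake is whether the viral load estimate can be used at all. The SAP wants effect sizes as preliminary evidence of efficacy, and a quantity that one person can reverse is a poor basis for that.

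**Working it through.** **Figures in the plan.** The total is 50 participants (Study Objectives). The significance level is 5% (SAP, last paragraph). There is no sample size derivation or viral load figure to reproduce, and the SAP says so of power: "While this study was not powered to detect significant differences".

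**Exact case.** Suppose 1 of 50 people goes from 20 to 100,000 copies/mL and the other 49 do not change (illustrative values, not from the documents).

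- Change c = 100,000 - 20 = 99,980
- Mean = c/50 = 1,999.6; median = 0
- SD = c/√50 = 14,139; SE = SD/√50 = c/50 = 1,999.6
- t = mean/SE = 1, p about 0.32 on 49 degrees of freedom

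The size of c cancels, so t is 1 in absolute value for a change of any size. With k equal changes in the same direction, t = √(49k/(50 - k)). For k = 2 this is √(98/48) = 1.43, also short of significance. One or two people can set the mean but, with everyone else unchanged, cannot make it significant.

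**Simulation, largest single change.** Inputs: 50 people; no true effect; suppressed values set to 20 copies/mL; viremic values lognormal with mean 3.5 log10, SD 1 and within-person SD 0.5; 5-30% viremic; run with and without people moving between suppressed and viremic. All of these except the 50 are assumptions.

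- Share of the total squared raw change carried by one person: median about 77-99%. Without status changes it was 99%, 94%, 87% and 83% at 5%, 10%, 20% and 30% viremic.
- Removing that person altered the sign of the mean, or left it at zero, in about 43-59% of trials.
- A one-sample t-test of mean change, as a stand-in for the regression, rejected in 0-1.3% of trials at a nominal 5%.

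With a narrower spread (between-person SD 0.8, within-person SD 0.4, status changes allowed) the one-person share was 94%, 82%, 74% and 69% at the same four viremic proportions. Moving the floor from 20 to 200 barely changed these shares.

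**Simulation, two largest changes, raw against log10.** Floor 20, half of viremic people staying viremic, total SD 0.3-0.9 log10 (assumed). Ranges are over the SD.

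| Viremic | Raw: share of top two | Log10: share of top two | Raw: sign altered | Log10: sign altered |
|---|---|---|---|---|
| 5% | 94-100% | 92-99% | 68-77% | 63-66% |
| 10% | 75-98% | 49-64% | 48-66% | 40-44% |
| 20% | 57-93% | 27-40% | 41-59% | 25-30% |
| 30% | 47-90% | 19-29% | 35-57% | 20-26% |

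Here "sign altered" means that dropping the largest one or two changes altered the sign of the mean or left it at zero. A log scale removes most of the dominance from about 20% viremic upward, but not at 5%, where only 50 × 0.05 = 2.5 viremic people are expected at a time point.

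**The second model.** Stating a distribution for the GENMOD model would not by itself solve this. The response can be negative, so a count or gamma distribution cannot be fitted to it directly, and a normal distribution with identity link is the linear model again.

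**Timing.** The model uses 8 and 16 weeks from the start of the intervention. Routine draws are not tied to those points, and the plan does not say which chart value is the baseline and which the follow-up.

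**The case against.** The strongest reply is that the harm is limited. Viral load is one of several exploratory outcomes in a pilot that disclaims power. The SAP also promises medians beside means, and a median change near zero would warn the reader. That stands, and it keeps the point away from the feasibility, alcohol and adherence results. It does not make the inferential model suitable, because the descriptive medians do not replace it.

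Three stronger readings are tempting, and the documents do not support them.

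- A reader might infer that one rebound or one re-suppression would be declared significant harm or efficacy. The exact case shows otherwise: the outlier inflates the standard error together with the mean. A point estimate could still be misread.
- A reader might infer that one or two people will certainly decide the result. That depends on the suppressed share, the spread of values and the assay limit, none of which is given. Only "could" is supported.
- A reader might infer false changes from assays switching during a long enrolment. The documents mention rolling enrolment, but neither its length nor any change of assay or limit.

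It is also fair to say that a log10 scale alone would remove much of the problem if viremia is common, and that a suppression table with few viremic people will itself rest on few discordant participants. Both stand, and the fix allows for them.

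**Conclusion.** The concern holds in a limited form. As written, the SAP's only inferential analysis of viral load is a linear model of raw change, in a treated population with no requirement for detectable virus. Under the assumptions shown, one person could carry a median of about 77-99% of the squared change at 5-30% viremic, somewhat less if viremic values are less spread out (69% at 30%). Removing that person alters the sign of the mean, or leaves it at zero, in about 43-59% of null trials.

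The consequence is an unstable and uninformative estimate with a test that rejects far less often than its nominal 5%. False significance is not the likely outcome. The textual part is firm. The size is conditional on a suppressed share, spread and reporting limit that had to be assumed, and the rejection rate comes from a one-sample stand-in for a regression whose covariates are not stated. The plan should be changed here, but the trial's main results do not depend on it.

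**What to change.** Take viral load out of the raw linear change model and specify the following in the SAP.

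1. **Main summary.** Report the proportion suppressed before and after the intervention, using one cut-off for everyone no lower than the highest reporting limit found in the charts. Cross-tabulate before by after, with exact 95% confidence intervals.
2. **Support.** Give log10 changes as a listing or supporting analysis, with values below the limit set to that common limit.
3. **Which values.** State for each group which chart value within its review window is "before" and which is "after", relative to the start of the intervention, and what happens when none qualifies. Without this rule the before/after table is undefined too.

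The cost is SAP wording, simpler tables and one extra field in the chart review (the reporting limit for each value). No further data are needed from participants. Dichotomising loses some information, which the log10 changes partly keep. The table may still rest on few discordant participants, and the exact intervals will show that openly.

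### The long-term model draws on two change scores per person, at 8 and 16 weeks, with no stated handling of within-person correlation; if both enter one ordinary regression, its standard errors are wrong.

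*Combined protocol and SAP*

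**What the plan says.** The last paragraph of the Statistical Analysis Plan covers long-term effects. It pools the arms: "participants from both the waitlist-control and intervention group will be combined into a single dataset". It then names two models. The first is a generalized linear model, to be run in GENMOD. For the second it says that "a multiple linear regression model will be fit to the change from baseline for each outcome measure".

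The dependent variable is defined once: "Change from baseline is the difference between the baseline value and values obtained at subsequent time points". Two time points follow, counted from the start of the intervention. The earlier one is given as "8 weeks (immediate post-intervention; T2 for intervention group and T3 for waitlist-control". The later one is given as "16 weeks (2 months post-intervention; T3 for intervention group and T4 for waitlist-control) for each outcome measure".

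The only reason given for modelling change is that "this model removes the effect of baseline differences that may exist from the model". The paragraph names no subject effect, REPEATED statement, covariance structure, robust standard error, time term, arm term or other covariate. It also does not say whether the two time points go into one model or two.

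Dependence between repeated measurements is mentioned once in the plan, for McNemar's test on the daily data: "This test will allow us to address the interdependency in the repeated measurements".

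**The concern.** The plan describes a single dataset, models specified per outcome, and two time points listed under one dependent variable. A programmer following this would most naturally build a file with up to two rows per participant. Both rows subtract the same baseline value, so they are correlated even if the two later measurements are only loosely related. Ordinary multiple linear regression treats rows as independent and has no term for this. GENMOD can handle it, but only if a REPEATED statement is specified, and none is.

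At stake is the precision attached to the question of whether any benefit lasts. Estimates that compare people, or average over them, would look more precise than they are. Comparisons between the two time points within a person would look less precise than they are. The plan applies a 5% level to all its tests, so the error would reach p-values as well as intervals.

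**Working it through.** The documents give no standard deviation, correlation or power figure for this analysis. The only figure of the plan's own to check is the nominal 5% level. All correlations below are assumptions, shown as a range.

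**Inputs.** N = 50 (section 3, Study Objectives), hence up to 2 × 50 = 100 rows per outcome if stacked. The test level is 5% (Statistical Analysis Plan, last paragraph). Sidedness is not stated; two-sided is assumed, with critical value 1.96.

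**Step 1: correlation of the two change scores.** Let each visit have the same variance. Let r0 be the correlation of baseline with each later value, and r12 the correlation between the two later values. Then

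ρ = (1 − 2·r0 + r12) / (2·(1 − r0)).

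- If r0 = r12, this is (1 − r0) / (2·(1 − r0)) = 0.5, whatever the common value.
- With r0 = 0.5 and r12 = 0.7, ρ = 0.7 / 1 = 0.7.
- With r0 = 0.6 and r12 = 0.5, ρ = 0.3 / 0.8 = 0.375.

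**Step 2: effect on stacked rows treated as independent.** For the mean change or an arm term, true SE / reported SE = √(1 + ρ). For an 8- versus 16-week contrast it is √(1 − ρ). The actual size of the test is 2·(1 − Φ(1.96 / ratio)).

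| ρ (assumed) | Ratio, mean change or arm | Reported SE too small by | Actual size | Ratio, 8 v 16 weeks | Actual size |
|---|---|---|---|---|---|
| 0.25 | 1.118 | 10.6% | 8.0% | 0.866 | 2.4% |
| 0.5 | 1.225 | 18.4% | 11.0% | 0.707 | 0.6% |
| 0.7 | 1.304 | 23.3% | 13.3% | 0.548 | 0.03% |
| 0.8 | 1.342 | 25.5% | 14.4% | 0.447 | below 0.01% |

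For ρ = 0.5: 1 − 1/1.225 = 0.184, and 2·(1 − Φ(1.96/1.225)) = 0.110.

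**Step 3: simulation check.** This used n = 50, complete data, two equal arms, no true effect and 4,000 runs per setting. The Monte Carlo standard error at 5% is √(0.05 × 0.95 / 4000) = 0.34 percentage points.

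- Ordinary regression on stacked rows, ρ = 0.5: size 10.5% to 11.9% for mean change and arm, 0.7% to 0.8% for the time contrast.
- The same with ρ = 0.7: 13.3% to 13.7% and 0.1%.
- Person-clustered robust SEs (variance scaled by 50/47, t on 47 degrees of freedom): 4.6% to 5.1% for all three terms.
- Mean change at one time point only, one row per person: 5.3% to 5.8%.

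The simulation agrees with the formulas. Either remedy restores a size of about 5%.

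**The case against.** The strongest reply is that the plan nowhere says the two time points are stacked. What it combines is participants across arms. Fitting each model separately at 8 and at 16 weeks is compatible with the text, and then there is no distortion from this source. This stands, and it makes the finding conditional.

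Naming GENMOD also does not imply independence, because GENMOD is one of the procedures that can do this correctly. That stands too, but it does not rescue the multiple linear regression, which is valid here only with one time point per model.

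A reader might go further and infer that the plan is in error on any reading, or that a loss of effect between 8 and 16 weeks is likely to be missed. The documents support neither. Treatment of rows as independent is inferred, not stated. The plan specifies no 8- versus 16-week contrast and no arm term, and a claim about what would be missed needs an effect size and a standard deviation, which are not given.

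Finally, this is a pilot. The plan says the study was not powered to detect significant differences (in the paragraph on the 8-week comparison), and with complete data the estimated mean change is the same either way. That limits the consequence. It does not remove it, since 5% tests are planned throughout and the stated aim is preliminary evidence of efficacy.

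**Conclusion.** The concern holds in conditional form. The plan defines two change scores per person on a shared baseline, names ordinary regression as one of its models, and says nothing about within-person correlation. On the natural reading, at an assumed correlation of 0.5, the standard error of the mean change (or of an arm term, if fitted) is understated by about 18%, and a 5% test rejects about 11% of the time under no effect. Across correlations of 0.25 to 0.8 the size runs from about 8% to 14%. A contrast of the two time points, if fitted, errs in the other direction. If each time point is modelled separately the distortion is zero.

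This is more than a missing detail: the wording permits both a valid and an invalid analysis, with error rates that differ about twofold at a correlation of 0.5, and one of the two named methods cannot handle paired rows at all.

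**What to change.** Replace the two models with one repeated-measures analysis per outcome, and state it in full. Either of these will do:

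- GENMOD with a REPEATED statement, participant as subject, and robust standard errors with a small-sample correction suited to N = 50. This also suits non-normal outcomes.
- PROC MIXED with unstructured covariance within participant and Kenward-Roger degrees of freedom.

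Include time since the start of the intervention (8 or 16 weeks), arm and the baseline value, and say which term or estimate answers the persistence question. Drop the separate multiple linear regression, or restrict it explicitly to one time point per model. If separate models per time point were always intended, one sentence saying so would remove this particular distortion.

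The cost is a small change of wording, with the same data and the same software. At a correlation of 0.5, intervals for the mean change would be about 22% wider than stacked ordinary regression would report (ratio 1.225), which is their correct width.
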